7.7.2.2 Imaging Restriction and Precautions

It is the local imaging facility's responsibility to determine, based on participant attributes (eg, allergy history, diabetic history, and renal status), the appropriate imaging modality and contrast regimen for each participant. Imaging contraindications and contrast risks should be considered in this assessment. Participants with renal insufficiency should be assessed as to whether or not they should receive contrast and if so, what type and dose of contrast is appropriate. Specific to MRI, participants with severe renal insufficiency (ie, estimated glomerular filtration rate < 30 mL/min/1.73 m²) are at increased risk of nephrogenic systemic fibrosis. MRI contrast should not be given to this participant population. In addition, participants are excluded from MRI if they have metallic implants, pacemakers, etc.

The ultimate decision to perform MRI in an individual participant in this study rests with the site radiologist, the Investigator, and the standards set by the local Ethics Committee.

7.7.3 Permitted Therapy

Participants are permitted the use of the following treatments:

- Topical, ocular, intra-articular, intra-nasal, and inhalational corticosteroids
- Adrenal replacement steroid doses ≤ 10 mg daily prednisone equivalent
- A brief (less than 1 week) course of corticosteroids for prophylaxis (eg, contrast dye allergy) or for treatment of non-autoimmune conditions (eg, delayed-type hypersensitivity reaction caused by a contact allergen)

7.7.3.1 Radiotherapy

Palliative and supportive care for disease-related symptoms may be offered to all participants on the trial; however, investigators should consult with the BMS Medical Monitor prior to initiating palliative radiation in participants who have not yet completed the DLT evaluation interval (Parts A and B).

The potential for overlapping toxicities with radiotherapy and BMS-986258 administered as monotherapy or in combination with nivolumab is currently not known. Therefore, palliative radiotherapy is not recommended while receiving any of these drugs, alone or in combination. If palliative radiotherapy in short courses and for isolated fields is required to control symptoms not clearly related to disease progression, then drug administration should be withheld, if possible, for at least 1 week before radiation and for at least 1 week after its completion. Participants should be closely monitored for any potential toxicity during and after receiving radiotherapy. Prior to resuming study drug treatment, radiotherapy-related AEs should resolve to \leq Grade 1 or baseline and participants must meet relevant eligibility criteria as determined by the BMS Medical Monitor in discussion with the Investigator. The BMS Medical Monitor must be consulted prior to re-initiating treatment in a subject with a dosing interruption lasting > 8 weeks after the last dose.

Details of palliative radiotherapy should be documented in the source records and eCRF. Details in the source records should include: dates of treatment, anatomical site, dose administered and

Protocol Amendment No.: 07

fractionation schedule, and AEs. Symptoms requiring palliative radiotherapy should be evaluated for objective evidence of disease progression. Participants receiving palliative radiation of target lesions will have the evaluation of best overall response (BOR) just prior to radiotherapy but such participants will no longer be evaluable for determination of response subsequent to the date palliative radiation occurs.

7.8 Treatment After the End of the Study

At the conclusion of the study, participants who continue to demonstrate clinical benefit will be eligible to receive BMS-supplied study treatment up to the maximum duration of 12 cycles as specified in Section 7.1. Study treatment will be provided via an extension of the study, a rollover study requiring approval by responsible health authority and ethics committee, or through another mechanism at the discretion of BMS.

BMS reserves the right to terminate access to BMS-supplied study treatment if any of the following occur: a) the study is terminated due to safety concerns; b) the development of BMS-986258 is terminated for other reasons, including but not limited to lack of efficacy and/or not meeting the study objectives; c) the participant can obtain medication from a government-sponsored or private health program. In all cases, BMS will follow local regulations.

8 DISCONTINUATION CRITERIA

8.1 Discontinuation From Study Treatment

Participants MUST discontinue IP (and non-IP at the discretion of the Investigator) for any of the following reasons:

- Participant's request to stop study treatment. Participants who request to discontinue study
 treatment will remain in the study and must continue to be followed for protocol-specified
 follow-up procedures. The only exception to this is when a participant specifically withdraws
 consent for any further contact with him/her or persons previously authorized by participant to
 provide this information.
- Any clinical AE, laboratory abnormality, or intercurrent illness which, in the opinion of the Investigator, indicates that continued participation in the study is not in the best interest of the participant.
- Documented disease progression as defined by RECIST v1.1 (Appendix 5) unless participants meet criteria for treatment beyond progression (Section 8.1.3).
- Clinical deterioration while receiving active study therapy that, in the opinion of the Investigator, indicates that continued participation in the study is not in the best interest of the participant.
- Any drug-related AE occurring at any time that meets DLT criteria as outlined in Section 7.1.1 will require permanent discontinuation. Exceptions to permanent discontinuation are listed in Section 7.4.2.
- Inability to comply with protocol.
- Discretion of the Investigator.
- Pregnancy.

Protocol Amendment No.: 07

Approved v2.0 930120074 9.0

- Termination of the study by BMS.
- Loss of ability to freely provide consent through imprisonment or involuntarily incarceration for treatment of either a psychiatric or physical (eg, infectious disease) illness. Note: Under specific circumstances and only in countries where local regulations permit, a participant who has been imprisoned may be permitted to continue as a participant. Strict conditions apply and BMS approval is required.
- Individual participants with confirmed CR will be given the option to discontinue study therapy on a case-by-case basis after specific consultation and agreement between the Investigator and BMS Medical Monitor in settings where benefit/risk justifies discontinuation of study therapy.

Any event that leads to delay in dosing lasting > 8 weeks from the previous dose requires discontinuation, with the following exceptions:

- Dosing delays for prolonged steroid tapers to manage drug-related AEs are allowed.
- Dosing delays lasting > 8 weeks from the previous dose that occur for non-drug-related reasons may be allowed if approved by the BMS Medical Monitor.

The assessment for discontinuation of nivolumab should be made separately from the assessment made for discontinuation of BMS-986258. Although there is overlap among the discontinuation criteria, if a participant in any of the combination arms meets criteria for discontinuation and the Investigator is unable to determine whether the event is related to both or one study drug, the participant should discontinue both nivolumab and BMS-986258 and be taken off the treatment phase of the study. An exception to the discontinuation of BMS-986258 can be made in the case of a nivolumab-related hypersensitivity or infusion reaction.

Specifically, for hypersensitivity or infusion-related reactions, because nivolumab is administered first, if a participant presents with a reaction before the administration of BMS-986258 has started, treatment with BMS-986258 may continue after the hypersensitivity or infusion-related reactions have been resolved. For other IMAEs, when signs or symptoms have developed after administration of both study drugs, if discontinuation criteria are met, both study drugs should be discontinued.

Refer to the Schedule of Activities for data to be collected at the time of treatment discontinuation and follow-up and for any further evaluations that can be completed.

In the case of pregnancy, the Investigator must immediately notify the BMS Medical Monitor/designee of this event. In the event a female participant becomes pregnant during a clinical trial, the study treatment must be discontinued immediately. Please call the BMS Medical Monitor within 24 hours of awareness of the pregnancy. If the Investigator determines a possible favorable benefit/risk ratio that warrants continuation of study treatment, a discussion between the Investigator and the BMS Medical Monitor/designee must occur. Refer to Section 9.2.5 Pregnancy.

Protocol Amendment No.: 07

All participants who discontinue study treatment should comply with protocol-specified follow-up procedures. The only exception to this requirement is when a participant withdraws consent for all study procedures including post-treatment study follow-up or loses the ability to consent freely (eg, is imprisoned or involuntarily incarcerated for the treatment of either a psychiatric or physical illness).

If study treatment is discontinued prior to the participant's completion of the study, the reason for the discontinuation must be documented in the participant's medical records and entered on the appropriate CRF page.

8.1.1 Temporary Discontinuation

Not applicable.

8.1.2 Rechallenge

Not applicable.

8.1.3 Treatment Beyond Progression

As described in Section 5.4.8, accumulating evidence indicates that a minority of patients with tumors treated with immunotherapy may derive clinical benefit despite initial evidence of progressive disease. The decision to continue treatment beyond investigator-assessed progression according to RECIST v. 1.1 should be discussed with the BMS Medical Monitor and documented in the study records. Participants with progressive disease may be permitted to continue study therapy provided the following criteria are met:

- Subject is deriving clinical benefit as assessed by the Investigator.
- Disease progression is not rapid as assessed by the Investigator.
- Subject continues to meet relevant eligibility criteria as determined by the BMS Medical Monitor in discussion with the Investigator.
- Subject tolerates study treatment.
- Subject has stable performance status.
- Treatment beyond progression will not delay an imminent intervention to prevent serious complications of disease progression (eg, central nervous system metastases).
- Participant provides written informed consent prior to receiving any additional nivolumab or BMS-986258 treatment, using an ICF describing any reasonably foreseeable risks or discomforts, or other alternative treatment options.

The assessment of clinical benefit should take into account whether the participant is clinically deteriorating and unlikely to receive further benefit from continued treatment. If the Investigator feels that the participant continues to achieve clinical benefit by continuing treatment with the study treatments, the participant should remain on the trial and continue to receive monitoring according to the Schedule of Activities All decisions to continue treatment beyond initial progression must be discussed with the BMS Medical Monitor, and an assessment of the

Protocol Amendment No.: 07

benefit/risk of continuing with study therapy must be documented in the study records (see Appendix 2).

For the participants who continue BMS-986258 (as a monotherapy or in combination with nivolumab) study therapy beyond progression, further progression is defined as an additional 10% increase in tumor burden with a minimum 5 mm absolute increase from time of initial PD. This includes an increase in the sum of diameters of all target lesions and/or the diameters of new measurable lesions compared to the time of initial PD. Nivolumab treatment should be discontinued permanently upon documentation of further progression.

New lesions are considered measurable at the time of initial progression if the longest diameter is at least 10 mm (except for pathological lymph nodes that must have a short axis of at least 15 mm). Any new lesion considered non-measurable at the time of initial progression may become measurable and therefore included in the tumor burden if the longest diameter increases to at least 10 mm (except for pathological lymph nodes that must have a short axis of at least 15 mm). In situations where the relative increase in total tumor burden by 10% is solely due to inclusion of new lesions that become measurable, these new lesions must demonstrate an absolute increase of at least 5 mm.

8.1.3.1 Discontinuation Due to Further Progression (Confirmed Progression)

Participants that meet the above criteria and continue on study therapy beyond initial progressive disease must discontinue BMS-986258 (and nivolumab, if part of the combination cohorts) upon the next documented event of progressive disease. A follow-up efficacy assessment should be performed at the next scheduled evaluation 8 weeks later (but no sooner than 4 weeks later) to determine whether there is continued progressive disease.

Subjects should discontinue study therapy upon further evidence of further progression, defined as an additional 10% or greater increase in tumor burden volume from time of initial progression (including all target lesions and new measurable lesions). The tumor burden volume from time of initial progression should be used as the reference baseline for comparison with the post-progression assessment. Any new lesion considered non-measurable at the time of initial progression may become measurable and therefore must be included in the tumor burden measurement as follows:

New lesions are considered measurable at the time of initial progression if the longest diameter is at least 10 mm (except for pathological lymph nodes, which must have a short axis of at least 15 mm).

[figure not shown]
For statistical analyses that include the investigator-assessed progression date, participants who continue treatment beyond initial investigator-assessed, RECIST v1.1-defined progression will be considered to have investigator-assessed progressive disease at the time of the initial progression event.

Subjects should continue to receive monitoring according to Study Assessments and Procedures described in Section 9. Radiographic assessment by CT (preferred) or MRI described in Section 9.1.1 is required when participants continue post-progression treatment. For participants that

discontinue post-progression treatment with study therapy, no additional radiographic assessments will be required.

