5.1.3 Treatment Period

The dosing regimen of BMS-986258 is Q4W.

Refer to Section 5.1 and

All participants will be treated for up to 96 weeks. The treatment period will consist of up to 12 treatment cycles (each cycle is 8 weeks in length). Following each treatment cycle, the decision to treat a participant with additional cycles of study therapy (up to a maximum of 12 cycles) will be based on response assessment at the end of each cycle. Continuous safety evaluation and tumor assessment (every 8 weeks [Q8W]) will guide the decision to treat a participant with additional cycles of study therapy if the participant has confirmed clinical benefit (up to a maximum of 96 weeks) for all study parts.

Study visits will be performed every 2 weeks for the first 8 weeks following the first dose of study treatment for the BMS-986258 Monotherapy Escalation (Part A), BMS-986258 with rHuPH20 SC for first dose (Part A1), and BMS-986258 in Combination with Nivolumab (Part B). Study visits at Cycle 2 and beyond will be every 4 weeks. During Cycles 1 and 3 of the treatment period, additional study visits to collect samples for intensive PK, ADA, required. See Section 9.5 for further details. In Part C (BMS-986258 in

Combination with nivolumab Cohort Expansion), study visits will be performed every 2 weeks for the first cycle. Study visits at Cycle 2 and beyond will be every 4 weeks.

In Part A (BMS-986258 Monotherapy Escalation), BMS-986258 will be administered Q4W. BMS-986258 will be infused according to dosing and infusion times in Table 7.1-1. Shorter infusion times may be used for initial dose panels and longer infusion times will be used for the higher dose panels.

In Part A1 (BMS-986258 SC for first dose), BMS-986258 will be co-administered with rHuPH20 for the first dose of BMS-986258 in Cycle 1. All subsequent doses will be administered as monotherapy IV Q4W. Alternatively, participants in cohort A1 who have received SC BMS-986258 on Cycle 1 Day 1 will be offered the option to receive subsequent IV combination therapy of BMS-986258 with nivolumab (480 mg) at the highest dose of BMS-986258 that has been shown to be safe and tolerable in the dose escalation (Part B). Treatment will be given Q4W twice per cycle, for up to twelve 8-week cycles (96 weeks).

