5.1.4 Follow-up

5.1.4.1 Safety Follow-up Period

Upon completion of study therapy (or up to a maximum of 96 weeks, if applicable), or once the participant has received the last administration of any study treatment (ie, at EOT), all participants will enter a safety follow-up period.

For participants who complete all scheduled cycles of therapy, the EOT visit will be the same visit as the last scheduled and completed on-treatment visit and will be the start of the safety follow-up period. For participants who do not complete all scheduled cycles of therapy, the EOT visit will be the most recent on-treatment visit (with all available safety and response data) and will not need to be repeated. Accordingly, for these participants, this visit will be considered the start of the safety follow-up period.

After the EOT visit, all participants will be evaluated for any new AEs for at least 100 days after the last dose of study treatment.

All participants will be required to complete the 3 clinical safety follow-up visits, regardless of whether new anti-cancer therapy is started, except those participants who withdraw consent for study participation.

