8.1.4 Exceptions to Permanent Discontinuation Criteria

Any drug-related AE occurring at any time that meets DLT criteria as outlined in Section 7.1.1 will require permanent discontinuation, with the exception of the following:

Any event that leads to a delay in dosing for BMS-986258 monotherapy or BMS-986258 in combination with nivolumab, lasting > 8 weeks from the previous dose, requires discontinuation, with the exception of the following:

- Dosing delays to allow for prolonged steroid tapers to manage drug-related AEs are allowed.
 Prior to re-initiating treatment in a participant with a dosing delay lasting > 8 weeks from the
 previous dose, the BMS Medical Monitor must be consulted. Tumor assessments should
 continue as per protocol even if dosing is delayed. Periodic study visits to assess safety and
 laboratory studies should also continue every 8 weeks, or more frequently if clinically
 indicated, during such dosing delays.
- Dosing delays lasting > 8 weeks from the previous dose that occur for non-drug-related reasons may not require discontinuation, if approved by the BMS Medical Monitor. Prior to

Protocol Amendment No.: 07

re-initiating treatment in a participant with a dosing delay lasting > 8 weeks, the BMS Medical Monitor must be consulted.

 Any AE, laboratory abnormality, or intercurrent illness which, in the judgment of the Investigator, presents a substantial clinical risk to the participant with continued nivolumab dosing.

All participants who discontinue IP should comply with protocol-specified follow-up procedures. The only exception to this requirement is when a participant withdraws consent for all study procedures including post-treatment study follow-up or loses the ability to consent freely (eg, imprisonment, involuntarily incarceration for the treatment of either a psychiatric or physical illness).

If study treatment is discontinued prior to the participant's completion of the study, the reason for the discontinuation must be documented in the participant's medical records and entered on the appropriate CRF page.

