2 RESPONSE CRITERIA

2.1 Evaluation of Target Lesions

• Complete Response (CR): Disappearance of all target lesions. Any pathological lymph nodes (whether target or non-target) must have reduction in short axis to < 10 mm.

- Partial Response (PR): At least a 30% decrease in the sum of diameters of target lesions, taking as reference the baseline sum diameters.
- **Progressive Disease (PD):** At least a 20% increase in the sum of diameters of target lesions, taking as reference the smallest sum on study (this includes the baseline sum if that is the smallest on study). In addition to the relative increase of 20%, the sum must also demonstrate an absolute increase of at least 5 mm. (Note: the appearance of one or more new lesions is also considered progression).
- **Stable Disease (SD):** Neither sufficient shrinkage to qualify for PR nor sufficient increase to qualify for PD, taking as reference the smallest sum diameters while on study.
- Not Evaluable (NE): If one or more target lesions cannot be measured or adequately assessed as either fully resolved or too small to measure (due to missing or poor quality images), and the sum of diameters of the remaining measured target lesions (if any) has not increased sufficiently to meet Progressive Disease as defined above.

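### Sections 8.1.3 and 8.1.3.1 give different triggers, and name different drugs, for stopping treatment beyond progression; Section 8.1.4 lists a substantial-risk event among the exceptions to discontinuation

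*Combined protocol and SAP*

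**What the plan says.** Section 8.1.3 covers participants who continue past initial progression on monotherapy or on the combination. It defines further progression as "an additional 10% increase in tumor burden with a minimum 5 mm absolute increase from time of initial PD", and refers to the sum of target-lesion diameters and the diameters of new measurable lesions. Its stopping instruction is "Nivolumab treatment should be discontinued permanently upon documentation of further progression".

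Section 8.1.3.1 gives two instructions of its own:

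- Participants "must discontinue BMS-986258 (and nivolumab, if part of the combination cohorts) upon the next documented event of progressive disease".
- Study therapy stops at further progression, defined there as "an additional 10% or greater increase in tumor burden volume from time of initial progression". Burden at initial progression is the reference for the later scan.

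Appendix 5, Section 2.1, defines PD in target lesions as at least +20% and at least +5 mm, "taking as reference the smallest sum on study (this includes the baseline sum if that is the smallest on study").

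On timing, Section 5.1.3 says "Continuous safety evaluation and tumor assessment (every 8 weeks [Q8W]) will guide the decision to treat a participant with additional cycles", with dosing Q4W. Under Section 5.1.4.1, after the last administration of study treatment, "all participants will enter a safety follow-up period".

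Section 8.1.4 lists exceptions to the rule that a dosing delay of more than 8 weeks requires discontinuation. The last item is an AE, laboratory abnormality or intercurrent illness that, in the investigator's judgment, "presents a substantial clinical risk to the participant with continued nivolumab dosing". Section 8.1 makes a similar event a mandatory reason to stop, and its own list of exceptions for long delays does not contain this item.

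**The concern.** Three instructions govern one decision, and they can point in different directions on the same scan. The two 10% definitions differ in scale (diameters or *volume*) and in whether a 5 mm minimum applies. The next-PD-event instruction is not tied to either of them. A site can comply with everything by stopping at the earliest trigger, but the Section 8.1.3 definition then has no effect. A site that continues under Section 8.1.3 may breach the mandatory wording in Section 8.1.3.1, and Section 9 allows no waivers.

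The drug to be stopped also differs. Section 8.1 asks for nivolumab discontinuation to be assessed separately from BMS-986258, so naming nivolumab alone in Section 8.1.3 is not neutral. Read by itself, that section names no drug that a monotherapy participant receives.

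What can vary between sites is exposure and the period in which AEs are collected. AE incidence is the primary endpoint (Section 4).

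The Section 8.1.4 item is a separate conflict of the same type: an event that Section 8.1 treats as a reason to stop is listed as an exception to stopping.

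**Working it through.** **Inputs.** Section 8.1.3: +10% and at least 5 mm from initial PD. Section 8.1.3.1: +10% from initial PD, no minimum in the defining sentence. Appendix 5, Section 2.1: +20% and at least 5 mm from the smallest sum. Section 5.1.3: scans every 8 weeks, doses every 4 weeks. The sums of diameters S below are illustrative.

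**The protocol's own conversion.** Appendix 5, Section 2.2.1.2, equates a 20% diameter increase with a 73% volume increase. Cubic scaling gives 1.20³ − 1 = 72.8%, so the figure is reproduced. On the same scaling, +10% diameter is 1.10³ − 1 = 33.1% volume, and +10% volume is 1.10^(1/3) − 1 = 3.23% diameter.

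**The two 10% rules.** With S the sum of diameters at initial PD:

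- Section 8.1.3: max(0.10 × S, 5 mm)
- Section 8.1.3.1, *volume* meaning amount: 0.10 × S
- Section 8.1.3.1, literal volume: 0.0323 × S (assumes uniform growth and no new lesions)

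| S (mm) | 8.1.3 (mm) | 8.1.3.1, amount (mm) | 8.1.3.1, literal volume (mm) |
|---|---|---|---|
| 20 | +5 | +2 | +0.65 |
| 30 | +5 | +3 | +0.97 |
| 40 | +5 | +4 | +1.29 |
| 50 | +5 | +5 | +1.61 |
| 60 | +6 | +6 | +1.94 |
| 100 | +10 | +10 | +3.23 |

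The 5 mm minimum binds when 0.10 × S < 5, that is, S < 50 mm. On the amount reading the rules differ below 50 mm and agree from there upward. On the literal reading they differ at every size shown.

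**The next PD event, read as Appendix 5 PD.** This comparison does not need the literal volume reading.

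- Smallest sum 50 mm: initial PD at 50 + max(0.20 × 50, 5) = 60 mm.
- Next scan unchanged at 60 mm: 60/50 − 1 = 20%, and 60 − 50 = 10 mm, so it is PD again.
- Section 8.1.3 is met at 60 + max(6, 5) = 66 mm; Section 8.1.3.1 (amount) at 1.10 × 60 = 66 mm.
- From 60 mm to under 66 mm, one sentence says stop and both 10% definitions say not yet.

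With a smallest sum of 25 mm, initial PD is at 25 + max(5, 5) = 30 mm, and the three triggers fall at 30 mm (unchanged scan), 33 mm (Section 8.1.3.1, amount) and 35 mm (Section 8.1.3).

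**Effect on treatment.** One scan interval is 8 weeks, and 8/4 = 2 doses. Each scan on which the rules disagree can therefore move the last dose by about one cycle, up to two doses.

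**Section 8.1.4 beside Section 8.1.** The lead-in governing the last item of Section 8.1.4 introduces exceptions to discontinuation, and no other lead-in applies to it. Section 8.1 lists a similar event under reasons for which participants must stop. Taken as written, the two conflict.

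**The case against.** The strongest points on the other side are these.

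- *Volume* is probably loose wording. Section 8.1.3.1 goes straight on to diameter-based measurability rules, and the 73% conversion belongs to participants with only non-measurable disease, whereas entry requires measurable disease. This is fair: the literal-volume column is conditional and the conclusion does not need it.
- The next PD event may simply mean further progression as defined in the following paragraph, with initial progression as the stated reference. That reading is possible, but the text does not say so, and the follow-up scan is described as checking whether progressive disease continues. A third reading, +20% measured from initial PD, would need +6, +10 and +20 mm at 30, 50 and 100 mm, later than either 10% rule. The direction of the gap thus depends on the reading.
- Section 8.1.3.1 sits under Section 8.1.3, so the 5 mm minimum could be inherited, and read together the sections cover both drugs. Text may also be missing after the new-lesion sentence. However, the defining sentence in Section 8.1.3.1 is complete without a minimum, and the nivolumab-only sentence stands.
- The Section 8.1.4 item has no list marker in this copy and is probably misplaced. It does not cancel the mandatory stop in Section 8.1. That limits its weight, but the conflict in the wording remains.
- The consequences are limited. Section 8.1.3.1 fixes the progression date for analysis at the initial event, the 28-day DLT window should be largely untouched, and safety follow-up runs from the last dose under any rule. Decisions to continue are discussed with the Medical Monitor, but that supplies no single definition.

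**Conclusion.** The concern holds, as an inconsistency in current operative text that should be fixed. The same scan can mean stop under one instruction and continue under another. On the reading most favourable to the plan (*volume* as amount, next PD event as the 10% event), the two definitions still differ for every sum below 50 mm at initial PD unless the minimum is taken as inherited, and the drugs named still differ. If the next PD event follows Appendix 5, the gap also affects larger sums: 60 mm to under 66 mm in the example.

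The size per disagreement is about one 8-week cycle, up to two doses, with a matching shift in the start of the 100-day safety follow-up. How many participants would be affected cannot be derived from the documents. PFS and DOR dates do not move. The literal-volume figures rest on uniform growth with no new lesions. The Section 8.1.4 conflict is real as written but probably a placement error.

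**What to change.** - Use one definition of further progression in Sections 8.1.3 and 8.1.3.1: the measurement scale, the relative threshold, and whether an absolute minimum applies.
- State how the next-PD-event instruction relates to that definition, including which scan is the reference for it.
- State which drug or drugs stop in monotherapy and in combination, identically in both sections.
- Reconcile the last item of Section 8.1.4 with the mandatory reasons in Section 8.1 and with the parallel exception list there.

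Which rule applies is for the sponsor to decide; the point here is only that the passages must agree. The cost is protocol wording, with no new assessments.
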